#### 5.4.2.1 Participant Monitoring and Removal from Study

Medical staff will assess and communicate with the study PI the appropriateness for continuation in the research study on a continuous basis and will remove from the trial participants with significant clinical deterioration or noncompliance of a type which could be dangerous. Criteria for removal from the study will include:

1. Clinical deterioration which cannot be managed safely in the context of outpatient treatment. This would include a participant who becomes suicidal, or a participant

who goes on severe drug binges (including non-opiate drugs), endangering him/herself.

- 2. Elevation of liver enzymes > 3 times normal. The PI or a study physician is available 24 hours/day by phone and/or beeper in case of emergency.
- 3. Participant becomes pregnant. In case of incidental pregnancy, the participant will remain in the study and will be followed until the resolution of pregnancy. To reduce unnecessary procedures, we will stop PK blood draws, unless clinically indicated, however the safety monitoring will continue. In addition, we will collect safety information related to the pregnancy and birth outcomes. After finding an incidental pregnancy the removal of the implant will be offered to the participant and the participant will decide how best to proceed in consultation with her obstetrician. The decision regarding the pregnancy will affect the decision whether or not to remove the implant at any point during the pregnancy. The risk of anesthesia differs during different times during pregnancy, however the risks of anesthesia and the risks of removal are both minimal.

If a participant becomes pregnant, PK labs will no longer be collected, but the participant will be followed for safety monitoring for the remainder of the study.

For those who withdraw from the study, (data collection and / or treatment) there are two main options:

- **Option 1:** Withdrawing from data collection and no further contact with study personnel. This carries the least amount of risk, with option 2 carrying some risk.

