- **Option 2:** Removal of the study medication via surgical procedure. Whilst removal of the study medication is straightforward in the early stages (up to about 10 days), removal after this becomes more complex as the OLANI biodegrades. Later procedures require a general anesthetic (with access to OR facilities) and may result in a large scar certainly larger than not removing the implant but the extent depends on the amount of tissue to be excised. The risks associated with general anesthetic vary between people, but about 20% of those receiving general anesthesia have minor AEs and 0.2% have major AEs including death. If removal of the implant is the only acceptable option to the participant, this will be arranged through either Columbia University Medical Center or another local hospital.

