## 8.4.3 Reporting of Pregnancy

Reporting of pregnancy will be to the treating physician, PI, NYSPI IRB and DSMB. After finding an incidental pregnancy the removal of the implant will be offered to the participant and the participant will decide how best to proceed in consultation with her obstetrician. The decision regarding the pregnancy will affect the decision whether or not to remove the implant at any point during the pregnancy. The risk of anesthesia differs during different times during pregnancy, however the risks of anesthesia and the risks of removal are both minimal.

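### The pregnancy text calls implant removal minimal-risk with no limit on time since implantation, but Option 2 of 5.4.2.1 says removal after about 10 days needs a general anesthetic, and the first scheduled pregnancy test is Day 28

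*Combined protocol and SAP*

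**What the plan says.** Section 5.4.2.1, item 3, covers a participant who becomes pregnant after receiving the implant. She stays in follow-up, removal is offered, and she decides with her obstetrician. The item then describes the risk: "The risk of anesthesia differs during different times during pregnancy, however the risks of anesthesia and the risks of removal are both minimal". Section 8.4.3, in the safety chapter, repeats the assurance: "however the risks of anesthesia and the risks of removal are both minimal". Neither place mentions how long the implant has been in.

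A little further on in 5.4.2.1, two options are set out, introduced by "For those who withdraw from the study, (data collection and / or treatment) there are two main options". Option 1 is to stop data collection and contact. Of it the protocol says: "This carries the least amount of risk, with option 2 carrying some risk". Option 2 is surgical removal. Here time since implantation matters: "removal of the study medication is straightforward in the early stages (up to about 10 days"), whereas "removal after this becomes more complex as the OLANI biodegrades". It continues: "Later procedures require a general anesthetic (with access to OR facilities) and may result in a large scar". It then gives rates for general anesthesia: "about 20% of those receiving general anesthesia have minor AEs and 0.2% have major AEs including death".

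Sections 7.2.1 and 7.3.5 and Table 7-1 set the testing schedule: a blood pregnancy test at Screening Visit 2, then urine tests at Day 28, Day 56 and the monthly visits from Day 90.

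**The concern.** The two descriptions of the same procedure do not agree. Read alone, the pregnancy passages tell staff that removal and its anesthesia carry little risk whenever they happen. Option 2 says this changes after roughly 10 days, when a general anesthetic and an operating room become necessary and a large scar is possible.

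At stake is the information used when removal is offered to a pregnant participant. She and her obstetrician have to weigh leaving the implant in against taking it out, and staff may use the protocol to brief them. If the usual case is a later removal, the assurance describes the exception. Nothing in the estimation of pharmacokinetic parameters or in any endpoint depends on it.

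**Working it through.** The plan gives no figure to reproduce. The check compares texts and then dates.

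**Inputs**
- Easy-removal period: up to about 10 days (5.4.2.1, Option 2), taken here as counted from implantation on Day 0.
- First scheduled pregnancy test after implantation: Day 28 (7.3.5; Table 7-1), window ±3 days.
- Later scheduled tests: Day 56 (±3 days) and the monthly visits from Day 90 (±10 days), with further tests at the Final Visit and any PK follow-up visit (Table 7-1).
- Visits at Day 0, 1, 2, 4, 8, 14 and 21: no pregnancy test in the schedule described in 7.2.1 and 7.3.5.

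**Text comparison**
- *Stage of pregnancy:* item 3 and 8.4.3 recognise that anesthetic risk varies with it. Option 2 does not discuss it.
- *Time since implantation:* item 3 and 8.4.3 are silent. Option 2 makes it decisive.
- *Level of risk:* item 3 and 8.4.3 call both risks minimal. Option 2 describes a harder procedure under general anesthesia after about 10 days, with rates of about 20% (1 in 5) for minor and 0.2% (1 in 500) for major adverse events of general anesthesia.
- *Cross-reference:* neither pregnancy passage points to Option 2.

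**Dates**
- Earliest scheduled test = 28 − 3 = Day 25. Latest date within the first window = 28 + 3 = Day 31.
- Gap between the end of the easy period and the earliest scheduled test = 25 − 10 = 15 days.
- Every later scheduled test falls further from Day 10, so the first test date settles the question.

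A removal prompted by a scheduled test therefore falls in the period for which Option 2 requires a general anesthetic. Early detection would not guarantee early removal either, because item 3 leaves the decision open throughout the pregnancy.

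**The case against.** The strongest reply is that the protocol already contains the right information close by. Option 2 follows item 3 in the same subsection. Its introduction reaches people who withdraw from treatment as well as from data collection, and having the implant taken out can be read as withdrawing from treatment. Item 3 itself stands in a list of criteria for removal from the study, and 5.4.2 names pregnancy among the reasons for discontinuation. This stands: a reader might infer that Option 2 cannot apply because a pregnant participant stays in the study, and the documents do not support that. It does not cure the conflict, because item 3 gives its own, different account without pointing to Option 2, and 8.4.3 sits in another chapter.

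A second reply is that *minimal* is undefined and that the assurance is not bare. Both points are fair. The sentence opens by conceding that anesthetic risk changes over pregnancy, so it would be wrong to say that it has no qualification. The gap is confined to time since implantation. Option 1's remark that removal carries some risk is also compatible with a minimal risk, so little rests on it.

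Third, only Option 2 states that late removal needs a general anesthetic. Section 7.6.2, Level 4, deals with removal after failed treatment of inflammation, which the section dates to after Day 14, and mentions only an incision over the implant site. Silence there does not contradict Option 2, but it is a reason for the sponsor to confirm the requirement when revising the text.

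Finally, a pregnancy could come to light before Day 10 through self-report or a test at an unscheduled visit. That is correct, and the point is limited to scheduled tests.

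**Conclusion.** The point holds as a minor correction to safety text. Sections 5.4.2.1 (item 3) and 8.4.3 give an assurance that ignores time since implantation, and Option 2 contradicts it for removals after about 10 days. Scheduled testing starts no earlier than Day 25, so a removal that follows a scheduled test falls under the later description.

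This rests on two assumptions: that the 10 days run from implantation, and that Option 2 is the sponsor's considered account of late removal. If Option 2 overstates what is needed, that text should change instead. The two accounts must agree either way.

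Three stronger conclusions are not supported. A reader might take the 20% and 0.2% rates as the risk of removal in a pregnant participant; they are quoted for general anesthesia in general. A reader might conclude that participants were misinformed; the consent form is not available, so nothing can be said about that. And a reader might suspect an effect on the results; no endpoint, sample size or analysis is touched. Few pregnancies are expected, with 10 women planned (5.3.1) and dual contraception required (5.2).

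**What to change.** In item 3 of 5.4.2.1 and in 8.4.3, delete the clause "however the risks of anesthesia and the risks of removal are both minimal" and keep the statement that anesthetic risk differs over pregnancy. Insert text to this effect:

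> Removal is simple for roughly the first 10 days after implantation. Beyond that it is more difficult, needs general anesthesia and operating-room access, and can leave a large scar whose size depends on how much tissue is taken out. Anesthetic risk differs from person to person. Option 2 of Section 5.4.2.1 gives adverse event rates for general anesthesia; they are not specific to pregnancy.

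The wording keeps Option 2's own caveats on scar size and individual anesthetic risk. The decision stays with the participant and her obstetrician.

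The cost is a few replacement sentences and a cross-reference in two places, plus the sponsor's confirmation that Option 2 is accurate for late removal. Visits, sample size, endpoints and analyses stay as they are.

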# 5.5 PREMATURE TERMINATION OR SUSPENSION OF STUDY

This study may be temporarily suspended or prematurely terminated if there is sufficient reasonable cause. Written notification, documenting the reason for study suspension or termination, will be provided by the suspending or terminating party to PI and sponsor. If the study is prematurely terminated or suspended, the PI will promptly inform the NYSPI IRB, (DSMB), FDA and will provide the reason(s) for the termination or suspension.

Circumstances that may warrant termination or suspension include, but are not limited to:

- Determination of unexpected, significant, or unacceptable risk to participants
- Insufficient compliance to protocol requirements
- Data that are not sufficiently complete and/or evaluable
- Determination of futility

Study may resume once concerns about safety, protocol compliance, data quality are addressed; and satisfy the Sponsor, NYSPI IRB, DSMB and FDA.

#### 6 STUDY AGENT

# 6.1 STUDY AGENT(S) AND CONTROL DESCRIPTION

#### 6.1.1 Acquisition

The OLANI will be supplied by Go Medical to the PI.

#### 6.1.2 Formulation, Appearance, Packaging and Labelling

#### 6.1.2.1 Manufacturing and Sterility

The OLANI is manufactured by Go Medical Industries Pty Ltd, [name].

[contact], Email: [contact]

The OLANI is manufactured under the code of GMP. Sterilization (gamma) validation of the product at 25KGy is performed in accordance with ISO 11173. Implants are sterilized with gamma radiation between a minimum of 25KGy and no more than 40KGy. Regular crushed bioburden tests are also conducted on randomly selected samples from each batch. Pyrogen testing is also performed on sterilized product at routine periods.

#### 6.1.2.2 Packaging

The OLANI is packed 10 pellets to one applicator device (Figure 6.1 and Figure 6.2). The applicator device is then sealed in a small foil pouch –Figure 6.3. This small foil pouch is then in turn sealed in another larger foil pouch –Figure 6.4. The double foiled pouch and applicator is labeled with a gamma indicator dot and the product label and sent for gamma sterilization. The gamma indicator dot will turn red when exposed to gamma radiation.

Figure 6.1: Applicator with OLANI pellets

Figure 6.2: Applicator with tablets exposed for delivery

Figure 6.3: First layer packaging

Figure 6.4: Second layer packaging

# 6.1.2.3 Disposal

The active implants shall be inserted into the subcutaneous tissue; however, the applicator device will be removed during the procedure and should be disposed of as per standard clinical protocols for biological specimens. The packaging can be disposed of in general waste.

#### 6.1.3 Product Storage and Stability

The investigational product is supplied sterile in a double layer of foil packaging. Storage conditions require temperature to be maintained between 8-30°C. Expiration dates are 24 months from date of sterilization by manufacturer and are listed on the second layer of packaging.

#### 6.1.4 Preparation

The investigational product is supplied sterile in foil packaging. The product will be prepared by the treating clinician using aseptic techniques to remove the applicator from the sterile packaging.

#### 6.1.5 Dosing and Administration

All participants will be administered a double dose (two syringes with 10 tablets (1.8 g) each) of the OLANI (\_\_\_\_\_). Investigational product will be administered surgically by the trial surgeon under local anesthetic. Subcutaneous insertion of the investigational product shall be documented as time = 0 for the purposes of pharmacokinetic blood collection.

#### 6.1.6 Route of Administration

Subcutaneous implant via small surgical procedure conducted under local anesthetic.

# 6.1.7 Starting Dose and Dose Escalation Schedule

All participants will be administered the same starting dose of 2 x OLANI (1.8g).

#### 6.1.8 Dose Adjustments/Modifications/Delays

Not applicable

# 6.1.9 Duration of Therapy

The duration of therapy will be 540 days.

#### 6.1.10 Tracking of Dose

All participants will be implanted with the study dose. At each scheduled follow-up visit an implant site evaluation will take place.

#### 6.1.11 Device Specific Considerations

Not applicable.

#### 6.2 STUDY AGENT ACCOUNTABILITY PROCEDURES

Go Medical will supply all study medication. The PI (or delegated study personnel) will sign that they have received all investigational product. Investigational product will be kept in a securely locked, temperature monitored cabinet and a drug inventory maintained. All unused supplies must be accounted for and returned to the sponsor in the event it is not used.

# 7 STUDY PROCEDURES AND SCHEDULE

#### 7.1 STUDY PROCEDURES/EVALUATIONS

#### 7.1.1 Study Specific Procedures

#### 7.1.1.1 Baseline Evaluation

Baseline evaluations will take place at the SURC, with two screening assessments being carried out, followed by a recruitment visit. The nature of the study and its risks and benefits will be explained to the participant by the PI who will also obtain a written informed consent from each potential participant prior to the administration of any study-specific procedures. The most important aspects of the protocol such as the implant procedure are discussed in great detail. The PI confirms that the participant is capable of providing informed consent.

At the first screening visit, informed consent for collecting information for screening will be obtained along with inclusion/exclusion criteria being assessed. The research physician will then perform tests as outlined in section 7.3.1.

At the second screening visit, medical staff or certified research assistants will collect blood and urine samples as outlined in section 7.3.2.

A recruitment visit will then be scheduled, where the research physician confirms that a participant meets all inclusion/exclusion criteria, is medically healthy to participate in the study. The physician also reviews and signs the inclusion/exclusion checklist and signs off on enrollment documentation. A procedure note for the medical chart will be included and signed verifying that the study physician reviewed results of the evaluation and obtained informed consent. Following study enrollment, the study physician assumes medical responsibility and arranging hospitalization for investigational product (IP) administration at CUMC followed by hospitalization at SURC.

#### 7.1.1.2 Naloxone challenge test (NCT)

All participants will undergo a NCT at SURC prior to IP administration. Prior to administration of the NCT, a baseline Clinical Opiate Withdrawal Scale (COWS) assessment will be obtained. Participants will receive 0.8 mg naloxone, IM, followed by q10 minutes observation by research psychiatrist or nurse over 30 minutes for signs and symptoms of opiate withdrawal. A COWS assessment will be repeated 10, 20, and 30 minutes after the administration of the NCT. If any COWS score increases more than 2 points from baseline, the participant will be considered a NCT failure and will not receive the IP.

Naloxone injection may cause withdrawal symptoms such as nausea, vomiting, diarrhea, stomach pain, fever, sweating, body aches, weakness, running nose, goosebumps, shivering, increased heart rate, and anxiety. Most of these effects will wear off after 20-30 minutes and treatment is usually not needed but in case of severe symptoms, participants will be offered a dose of clonidine 0.1 mg and/or clonazepam 0.5 mg. In that case, participants will be monitored for up to 6 hours until all symptoms resolve, and they can be released.

If a participant passes the NCT then they will progress to the IP administration with the implantation procedure 7.1.1.3.

## 7.1.1.3 Implantation Procedure

The investigational product will be administered via a minor surgical procedure conducted at CUMC by the study surgeon [name] who is a board certified plastic surgeon. Prior to the procedure participants will be fitted with an intravenous cannula to aid blood collection during the first 48 hours of sampling. The surgical procedure will take approximately 30 minutes and will be performed under local anesthesia. The surgical procedure will be carried out by the study plastic surgeon trained in the implantation procedure (see 1.7) supported by a clinical nurse and another support staff.

- Step 1: Have the participant lie on their back on an appropriate operating table
- **Step 2:** Disinfect hands with approved validated procedures for the institution where the procedure is being carried out then apply non-sterile gloves.
- **Step 3:** Administration of intra-operative prophylactic antibiotic. There is good literature evidence for intra-operative prophylactic antibiotics with breast and other implants. For this reason, the participant will be given 2g of IV cefazolin (600 mg clindamycin if allergic to cephalosporins or penicillin) within 30 minutes preceding the surgery.
- **Step 4:** The participant's abdomen is carefully observed and palpated with a view to defining the most ideal surgical site. The usual placement of the OLANI is in V-shape (see Figure 7.1) with one implant on either side.

[figure not shown]
[figure not shown]

Figure 7.1: Usual OLANI placement

**Step 5:** Using a new disposable marker pen, define the area that the local anesthetic will be injected into (Figure 7.2). The outer limit of the anesthetic is defined by the outer lines and two single lines mark the center of the site. The two central lines guide the position that the original lidocaine is inserted into. The outer lines indicate the area that the 40 mL of bupivacaine is inserted into.

#### Figure 7.2: Target insertion of local anesthetic

- **Step 6:** Following the drawing of the lines, the skin is prepared with betadine (or chloraprep if allergic to iodine). When this has dried a disposable sheet is applied carefully to cover the participant's underpants which will allow exposure of the symphysis pubis. Shaving can occur if any of the pubic or abdominal hair is close to the area marked.
- Step 7: Administration of local anesthetic.

A total of 60 mL local anesthetic will be administered to cover the left and right-hand side of the abdomen. This shall consist of 20 mL of 0.5% lidocaine followed by 40 mL of 0.25% bupivacaine with adrenalin. The 20 mL of lidocaine is inserted initially with a 25 or 26 gauge needle very slowly along the marked two central lines. It is important to administer this very slowly to minimize the participant's discomfort. Initially 2mL is administered over several minutes without causing significant discomfort. After 2mL has been administered, remove the 25 or 26 gauge needle and change to a 1.5" or 2" (40 mm or 50 mm) 21 or 22 gauge needle. This new needle is carefully inserted into the subcutaneous tissues where the initial 2mL of local anesthetic had been inserted. 9mL of lidocaine can then be administered into the subcutaneous tissues on the left side of the abdomen and then the remaining 9mL can then be administered to the subcutaneous tissue on the right-hand side of the abdomen. The technique of inserting the initial 9 mL guided by the two marked central lines and the technique of pushing the subcutaneous tissues toward the needle allows the local anesthetic to be concentrated in the area between the sheath and the subcutaneous tissues. After the insertion of the lidocaine 20 mL of 0.25% bupivacaine with adrenaline is inserted into the subcutaneous tissue on the left side of the abdomen and another 20mL to the subcutaneous tissue right side of the abdomen to cover the area described in Figure 7.2.

Step 8: Preparation of the site following local anesthetic administration.

It is advised to wait 10 minutes following insertion of local anesthetic in order to maximize the benefit of the local anesthetic prior to commencing the surgical procedure. The site is cleaned again with betadine. The surgeon then cleans their hands

again and puts on sterile gloves. The site should then be allowed to dry before surrounding the operative site with sterile towels or drapes.

Step 9: Surgical procedure

The surgical procedure commences by using a scalpel, blade size 15, where the skin at the center of the site is stretched and a 10-12 mm incision approximately 1-2 mm deep is created. This initial incision will simply be partially through the skin and so the blade is then reversed, and a firm incision is made approximately 5-10 mm deep while the reverse blade is used to cut completely through the skin along the 10-12 mm incision line.

